### 9.3.2 ANALYSES OF PRIMARY OUTCOMES

The primary outcome will be the number (proportion) of prescriptions triggering notifications that were changed within 7 days, among all prescriptions that triggered a notification.

As noted in the general approach, for the primary factor (existing-prescription notifications), main effect analyses will compare the proportion of DOAC prescriptions that were changed within seven business days following the notification between prescribers randomized to receive the notifications themselves vs. prescribers for whom notifications were sent directly to anticoagulation clinic pharmacists.

---

### 9.3.3 ANALYSES OF SECONDARY OUTCOME

Secondary outcomes will be the number (proportion) of new DOAC prescriptions triggering alerts that were changed within 7 days, among all prescriptions that triggered an alert.

As noted in the general approach, for the secondary outcome factor (new DOAC prescription alerts), main effect analyses will compare the proportion of DOAC prescriptions that were changed within seven business days following the notification between prescribers randomized to receive enhanced alerts vs. enhanced alerts plus pharmacist referral.

---

### 9.3.4 ANALYSES OF IMPLEMENTATION

**Reach:** To assess reach, we will examine the proportion of patients on DOACs that had alerts or notifications fire, as well as the proportion of prescribers that received alerts and/or notifications. To further understand reach, we will also report the proportion and clinical predictors of prescribers who dismissed alerts or notifications (defined as no action within seven calendar days). We will also identify the proportion and predictors of prescribers who used anticoagulation clinic pharmacist referrals in new-prescription alerts. We will also categorize all DOAC alerts based on prescriber and patient characteristics (e.g., demographics, comorbidities).

**Effectiveness:** Analysis of Effectiveness will be the focus of the primary and secondary outcome measures (as noted above). We will evaluate the effectiveness of our DOAC alert system components by examining patient-level clinical adverse event rates (bleeding and thrombotic) within 30 days of triggering the alert. This time period was selected to minimize potential contamination from the safety review mechanism described above, and we recognize that rates for the adverse events will be low.

However, as a T4 implementation study, the primary goal is implementing the evidence-based practice for which efficacy is already established. Supplementary analyses will also examine the effect of the alert system overall on adverse events.

Clinical adverse events assessed will include major and clinically-relevant non-major bleeding (CRNMB) events, as defined by the International Society on Thrombosis and Haemostasis (ISTH), new or recurrent VTE events, and stroke or systemic arterial embolic events objectively identified by imaging and identified as a new event by their primary clinical provider. Transient Ischemic Attacks (TIAs) that do not result in findings on imaging (such as CT or MRI) will not be included. Each of these events will be captured using health informatics tools (described below) and adjudicated every six months. Adjudication will occur at least one month prior to six month DSMB meetings to allow for the DSMB to review findings in advance of the meeting. We will use Michigan Medicine-developed health informatics tools to create a report that identifies all patients whose prescribers have received an alert or notification and any adverse event diagnosis codes within 30 days thereafter. These cases will then be reviewed by the adjudicators to determine if an adverse event occurred and if it was associated with medication management, as defined in Section 8.4.2.2. The adjudicators will have access to all laboratory and medication data as well as clinical notes, but will be blinded to group allocation. The report, created by Michigan Medicine health informatics research team, will undergo a validation process for accuracy by the study team leads, including a cardiovascular physician and pharmacist.

**Implementation** (including fidelity): To address how various EHR alerts impact implementation of evidence-based DOAC prescribing, we examine process measures related to prescriber and pharmacist alert receipt. For prescribers, we will examine how often they order (or do not order) the medication recommended by the alerts (and, for the latter, whether they provide a reason) for both new-prescription alerts and existing-prescription notifications. For pharmacists, we will measure how often they respond to referrals at the time of initial prescribing or to existing prescription notifications, as well as the time from referral/alert until the pharmacist documents a recommendation in the EHR. For existing prescription notifications, we also will measure the time from notification until the notification is read as well as time until any DOAC prescription change or related EHR documentation occurs as well as the number of times a existing-prescription notification is read before being acted on.

**Maintenance:** To measure maintenance and sustainment, we will assess all “reach” and “adoption” outcomes after 6 and 12 months for all patients, and after 18 months for the subset of prescribers enrolled prior to the second quarter of Year 2 (approximately N=225, or 75% of the total prescriber enrollment). This will also allow us to investigate whether treatment effects for prescribers are maintained after the initial adoption.

**Other implementation outcomes:** We will also estimate the resource utilization by the pharmacists using a combination of EHR tool tracking (measured in hours) and self-reported weekly hours dedicated to study activities using a study provided tracking sheet similar to those used in our prior implementation trials (R01MH099898; R01MH114023).

---

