## 6.3 MEASURES TO MINIMIZE BIAS: RANDOMIZATION AND BLINDING

Participants will be randomized by computer based solely on the sampling algorithm, so unintended selection bias by the study team will not be a factor. The randomization algorithm will stratify by:

1. Trainee vs non-trainee specialist vs non-trainee pcip
2. Alert vs notification

This clinical trial is not fully blinded. Participants randomized to the different alert and notification conditions and will be blinded to the specifics of their assignment. However, they may be able to discern which condition they have been assigned to owing to the specifics of the alerts and notifications they receive. During the data analysis, study team members will be blinded to the alert and notification condition of the participants.

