**Secondary**

Our **secondary** outcome measure (adoption) is the proportion of DOAC alerts that lead to a change in the prescription within seven days. The denominator is the total number of DOAC prescription alerts with or without a visible option for pharmacist consultation (per randomization). The numerator is the number of DOAC alerts that result in any change to the DOAC prescription within seven days after the alert has occurred.

**Effectiveness:** We will evaluate the effectiveness of our DOAC alert system components by examining patient level 30-day clinical adverse event rates (bleeding and thrombotic). This time period was selected to minimize potential contamination from the safety review mechanism described above, and we recognize that rates for the adverse events will be low. Supplementary analyses will also examine the effect of the alert system overall on adverse events.

Clinical adverse events assessed will include major and clinically-relevant non-major bleeding (CRNMB) events, as defined by the International Society on Thrombosis and Haemostasis (ISTH), new or recurrent VTE events, and stroke or systemic arterial embolic events. Each of these events will be captured using health informatics tools (described below) and independently adjudicated by two expert clinicians (one pharmacist, one prescriber) who meet once in Y1 and twice in Y2 to adjudicate any potential adverse events. We will use two Michigan Medicine-developed health informatics tools, DataDirect and EMERSE, to identify adverse events and capture clinical data (e.g., notes, labs, imaging, procedure reports) for adjudication. These tools allow for rapid identification of populations based on granular clinical details (e.g., demographics, diagnosis, medication use) and for textbased searches of the medical record for key terms (e.g., “bleeding”, “stroke”) across pre-defined patient populations. The adjudicators will be blinded as to which alert the patient’s prescribing clinician was randomized. Using these EHR search tools, we can also capture all ICD10 diagnosis and procedure codes for longitudinal system-level analyses. [See Appendix A for current list of ICD10 codes used.]

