#### 8.4.2.1 SEVERITY OF EVENT

The following guidelines will be used to grade severity of AEs:

Bleeding related events, as defined by the International Society on Thrombosis and Haemostasis (ISTH):

- Major,
- clinically relevant, non major
- minor

Thrombotic (stroke and venous thromboembolism):

- There will be no severity grading of thrombotic events.

Any bleeding or new thrombotic event that occurs within 30 days of a study alert or notification will be included as an adverse event.

Serious adverse events include any death or life threatening outcome. This includes ISTH major bleeding event and any new thrombotic event that occurs within 30 days of a study alert or notification.

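### Section 9.3.4 counts an imaging-positive stroke or embolism only if an undefined provider called it new; Sections 8.1 and 8.4.2.1 carry no such condition

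*Combined protocol and SAP*

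**What the plan says.** Section 9.3.4 (Effectiveness) lists the clinical events for analysis and qualifies one group of them: strokes and systemic arterial emboli must be "objectively identified by imaging and identified as a new event by their primary clinical provider". The two conditions are joined, so both must be met. The same paragraph hands the decision to the adjudicators: "These cases will then be reviewed by the adjudicators to determine if an adverse event occurred and if it was associated with medication management". It adds: "The adjudicators will have access to all laboratory and medication data as well as clinical notes, but will be blinded to group allocation". It does not define the primary clinical provider.

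Section 8.1 (Effectiveness) describes the same outcome as "new or recurrent VTE events, and stroke or systemic arterial embolic events". It has two expert clinicians, one pharmacist and one prescriber, adjudicating independently. It sets neither an imaging condition nor a provider condition for stroke or embolism.

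Section 8.4.2.1 includes among serious adverse events "any new thrombotic event that occurs within 30 days of a study alert or notification". It does not say who decides that an event is new.

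On who the provider might be, the Synopsis makes the DOAC prescriber the trial participant, and Section 5.1 names primary care clinicians among the prescribers covered. Section 6.3 says participants are meant to be blinded to the specifics of their assignment, but that "they may be able to discern which condition they have been assigned to". Section 9.1 treats clinical effectiveness as a secondary outcome.

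**The concern.** The plan arranges for blinded adjudication and then, in one section, attaches a condition met or failed by someone outside the adjudication. If that person's note is silent, or describes the lesion as old, the literal rule leaves an imaging-positive event out whatever the adjudicators conclude from the record. The person is not identified, and the randomised prescriber is not excluded.

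The conflict between sections matters whoever the provider is. The same stroke could be a serious adverse event under Section 8.4.2.1 and a non-event under Section 9.3.4. The adjudication in 9.3.4 is timed to supply the DSMB meetings and applies the categories of Section 8.4.2.2. That section also uses adverse events to ask whether the 15-day dashboard embargo contributed to harm. Section 9.3.6 allows the trial to be halted or modified if adverse events differ between arms at p < 0.01. The plan does not say which definition of a thrombotic event governs these uses.

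**Working it through.** **The definitions side by side (stroke and systemic embolism)**

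| Section | Imaging required | Must be new | Who judges newness |
|---|---|---|---|
| 8.1 | not stated | not stated | not stated; two adjudicators review the event |
| 8.4.2.1 | not stated | yes | not stated |
| 9.3.4 | yes | yes | an undefined primary clinical provider; adjudicators determine whether an event occurred |

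**Two test cases**

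1. A stroke is seen on imaging within 30 days of a notification. The adjudicators judge it new, but the provider's note does not call it new. Under 8.1 it is in the listed category and goes to the adjudicators. Under 8.4.2.1 it counts if whoever judges newness agrees. Under the literal wording of 9.3.4 it fails the second condition. Nothing says whether the adjudicators may count it anyway.
2. The provider calls an event new, but the adjudicators find no event. Section 9.3.4 still leaves that decision with the adjudicators, so the label does not force the event in.

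The label can therefore exclude but not include, which makes it a one-way veto on the literal reading. Whether the qualifier also reaches venous thromboembolism, earlier in the same sentence, is grammatically unclear.

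**Scale**

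No stated figure decides the point. These numbers show only how few events are expected.

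- Inputs (Section 9.1): 300 prescribers, so 150 per arm; 2 patients each on average (3 in the less conservative case); 1% versus 0.5%; ICC 0.03; stated power 63% with 2 patients and 79% with 3.
- Check of the stated power: n_eff = n / [1 + (m − 1) × 0.03], which is 300/1.03 = 291.3 for m = 2 and 450/1.06 = 424.5 for m = 3. Power = Φ[(|p1 − p2| − 1.96 × SE0) / SE1], where SE0 is the pooled and SE1 the unpooled standard error, two-sided alpha 0.05. At 1% versus 0.5% this gives 10.4% (m = 2) and 13.2% (m = 3). At 10% versus 5% it gives 63.0% and 79.1%, matching the stated figures. The printed rates and printed power do not belong together. That is a separate matter, but it means the scale should be shown for both pairs of rates.
- Expected events of all types per arm, 2 patients per prescriber: 300 × 0.01 = 3.0 and 300 × 0.005 = 1.5. With 3 patients: 4.5 and 2.25. At 10% and 5% with 2 patients: 30 and 15.
- One excluded event moves an arm's rate by 1/300 = 0.33 points. That is 0.33/0.5 = 67% of the difference at 1% versus 0.5%, and 0.33/5 = 7% at 10% versus 5%.
- Events lost to the condition per arm = 300 × rate × s × f, where s is the share of events that are stroke or embolism and f is how often the condition fails. The documents give neither. Assuming s from 0.25 to 0.75 and f from 0.1 to 0.5, at a 1% rate the loss runs from 300 × 0.01 × 0.25 × 0.1 = 0.08 to 300 × 0.01 × 0.75 × 0.5 = 1.1 events.

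**The case against.** The strongest answer is that Section 9.3.4 leaves the decision to blinded adjudicators with access to the notes, and that the provider phrase may simply describe the evidence they look for. The term could mean the clinician who treated the event, not the prescriber. Sections 8.1 and 9.3.4 could be read as a general list and a fuller version of it, and 8.4.2.1 also requires newness. A newness test also has a purpose, since it screens out old lesions found incidentally.

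Much of this stands, and it limits what can be claimed. A reader might infer that a trial participant can override the adjudication. The documents do not say so: they are silent on disagreement, and the label can at most exclude. A reader might call the prescriber unblinded, but Section 6.3 says only that the condition may be discernible. That the provider is the randomised prescriber is possible, not stated. A reader might also expect labelling to differ by arm because pharmacists are involved or because reputations are at stake. No text supports a difference by arm, and Section 2.3.4 answers the reputational risk listed in 2.2.1 with de-identified data and aggregate reporting. Finally, the two-thirds figure is not a measure of bias. It covers all event types and rests on rates that do not fit the plan's own power.

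The objection does not remove the joined conditions, the undefined term, the silence on who prevails, or the mismatch with 8.1 and 8.4.2.1. These remain even if the provider is the treating clinician.

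**Conclusion.** The point holds as a defect in one outcome definition. On its literal wording, Section 9.3.4 makes an undefined provider's label necessary for a stroke or systemic embolism to count. The two other sections that define these events do not. The reach is limited to the stroke and embolism component of a secondary and safety outcome. Bleeding follows the ISTH definitions, and the primary endpoint does not use these events.

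The size cannot be stated. How often the condition would fail, and whether that would differ by arm, is unknown from the documents. If it failed equally often in both arms, and stroke and embolism made up the same share of events in each, both rates would shrink by the same factor and their ratio would be unchanged. At the printed rates so few events are expected that a single exclusion would be noticeable; at 10% versus 5% it would matter much less. This is a cheap improvement, not a threat to the trial's main conclusion.

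**What to change.** Keep the requirement that a stroke or embolism be new, but make it a finding of the two blinded adjudicators, reached from imaging reports and clinical notes. Treat the provider's note as evidence and not as a requirement. Use one stroke and embolism definition in Sections 8.1, 8.4.2.1 and 9.3.4, and state whether the imaging and newness requirements also apply to venous thromboembolism. Section 8.1 already lists imaging among the data captured for adjudication; the access sentence in 9.3.4 should list it too.

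The cost is wording. The adjudicators already review these cases, so no new data are needed. The downside is a few more cases in which they must judge old against new lesions themselves.

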### 9.3.5 EXPLORATORY ANALYSIS

#### **Interrupted time-series analyses** (comparison to usual care).

While our trial and analyses are designed to determine the best approach for improving evidence-based DOAC prescribing through EHR alerts via comparative effectiveness analyses, observational analyses can also evaluate the impact of the introduction of the DOAC EHR alert system overall on patient receipt of evidence-based DOACs, relative to prior to the trial. Using EHR data, we will compute the proportion of patients that were receiving an inappropriate DOAC for each quarter, starting 24 months prior to randomization and continuing 18 months after randomization. Interrupted time series analyses (ITSA) will then be used to compute the change in inappropriate DOAC prescriptions, pre- and post-system introduction, to determine whether the system implemented via the trial resulted in a significant decline in patients on inappropriate DOACs. We will also assess for system-level changes in adverse event rates, as defined in the Measures section. As a further check on changes in DOAC prescribing behaviors in response to the alerts and/or increased prescriber-pharmacist collaboration, we will also use ITSA models to assess for changes in the rate of new-prescription alerts (per total number of DOACs prescribed) over the 18-month study period, relative to the 24-month period prior to study start.

#### **Moderator analyses.**

Moderator analyses will be used to help pinpoint the prescriber- and patient-characteristics that most benefit from alerts designed to facilitate prescriber-pharmacist collaboration for both the new-prescription alerts and existing-prescription notifications. We hypothesize that for both new-prescription alerts and existing-prescription notifications, alerts and notifications that engage pharmacists will be more effective at improving patient receipt of evidence-based DOACs for prescribers that (1) are based in primary care vs. medical specialists and/or (2) have prescribed fewer DOACs in the six months preceding randomization; and for patients that (1) are aged 70+; (2) have a VTE (as opposed to AF) diagnosis, as the former has more complex dosing that many clinicians are less familiar with; (3) have 5+ concurrent medication prescriptions; and/or (4) have moderate or worse renal function (creatinine clearance  $\leq 60$  ml/min). Moderators will be assessed by adding interaction effects between the treatments and the moderator(s) of interest to the primary analysis model described above. All tested moderators will be reported and those that show both clinical and statistical significance will be considered for use in tailoring alert delivery.

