For our secondary prescriber-level outcomes, we will have 94% power to detect a difference in proportions of 0.4 to 0.6. For longitudinal outcomes (e.g., maintenance), this calculation is conservative as it does not account for repeated measures. For our clinical effectiveness secondary outcome, we will have 63% power to detect a difference of 1% vs. 0.5% in adverse event rates for each factor, again assuming 300 prescribers with an average of 2 patients each, and assuming a prescriber-level ICC of 0.03 (for clinical adverse events). A less conservative estimate of 3 patients per prescriber increases this power to 79%

For our exploratory moderation analyses, described below in Section 9.3.5, again assuming 300 prescribers with 2 patients each and an ICC of 0.1, we will have 80% power to detect a minimum effect size of 0.34 for our binary prescriber-level moderators, using a two-sided test with  $[\alpha] = 0.05$ . If our average number of patients per prescriber is 3, this minimum detectable effect size decreases to 0.29 under the same assumptions. For our binary cross-level (patient-level) moderators, assuming a non-randomly varying slope, with an average of 2 patients per prescriber, we will have 80% power to detect a minimum effect size of 0.34; assuming 3 patients per prescriber decreases this minimum detectable effect size to 0.27. Minimum detectable effect sizes for cross-level moderators that also include a random slope are slightly larger at 0.36 and 0.28 respectively

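### Age, medication count and creatinine clearance are tested as moderators only through single cuts, and prior DOAC volume is left undefined; if the effects are graded, continuous interaction tests would be more powerful at almost no cost.

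*Combined protocol and SAP*

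**What the plan says.** The moderator paragraph of Section 9.3.5 names two prescriber-level and four patient-level moderators of the benefit of involving a pharmacist.

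- **Binary by nature:** primary care versus specialist, and VTE versus AF.
- **Numeric but cut once:** age (70 or over), and the two in "have 5+ concurrent medication prescriptions; and/or (4) have moderate or worse renal function", the renal one defined as creatinine clearance of 60 ml/min or less.
- **Numeric with no cut given:** prescribers who "have prescribed fewer DOACs in the six months preceding randomization".

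Each moderator is tested by adding its interaction with treatment to the primary mixed logistic model. All tested moderators will be reported. Those that matter both clinically and statistically may later inform how alerts are targeted.

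Section 9.1 states power for these analyses only in binary form. At prescriber level, "we will have 80% power to detect a minimum effect size of 0.34 for our binary prescriber-level moderators", "again assuming 300 prescribers with 2 patients each and an ICC of 0.1". With three patients each the figure becomes 0.29. The patient-level statement opens "For our binary cross-level (patient-level) moderators, assuming a non-randomly varying slope, with an average of 2 patients per prescriber" and gives 0.34, or 0.27 with three patients. No power is stated for a continuous moderator.

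**The concern.** The hypotheses read as graded: less prescribing experience, older age, more drugs and poorer renal function should each make pharmacist involvement more useful. A single cut treats patients aged 69 and 71 as different, and patients aged 71 and 90 as alike. No reason is given for 70 or for five drugs as effect-modifying points. The renal cut is tied only to a named category of impairment.

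Prior DOAC volume has a different gap. Section 9.1 implies two levels for prescriber-level moderators, yet Section 9.3.5 does not say where fewer begins. Either a cut will be chosen later, possibly with the data in view, or the test will be continuous and has no power statement.

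At stake is whether a graded effect is found, and whether later targeting of pharmacist-engaging alerts rests on an unexplained threshold.

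**Working it through.** **1. Inputs.** From Section 9.1: 300 prescribers, 150 per arm; 2 or 3 patients each; ICC 0.1; two-sided alpha 0.05; 80% power at 0.34 or 0.29 (prescriber level) and 0.34 or 0.27 (patient level), all for binary moderators. Not in the documents, so assumed: a roughly normal moderator (for counts, after a log transform), a linear interaction, a share q of 20% to 50% on the smaller side of the cut, and no variance explained by covariates.

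**2. The plan's own figures.** The sum of normal quantiles for 80% power is 1.960 + 0.842 = 2.802. I used the standard two-level formulas with a 50/50 moderator, for which 0.5 × 0.5 × 0.5 × 0.5 × 300 = 18.75.

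- Prescriber level, 2 patients: 2.802 × √[(0.1 + 0.9/2)/18.75] = 2.802 × 0.1713 = 0.48 (plan: 0.34).
- Prescriber level, 3 patients: 2.802 × √[(0.1 + 0.9/3)/18.75] = 0.41 (plan: 0.29).
- Patient level, fixed slope, 2 patients: 2.802 × √[0.9/(18.75 × 2)] = 2.802 × 0.1549 = 0.43 (plan: 0.34).
- Patient level, fixed slope, 3 patients: 2.802 × √[0.9/(18.75 × 3)] = 0.35 (plan: 0.27).

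The stated values do not reproduce from the stated inputs. The prescriber figures match if the variance is halved by something unstated, such as covariates explaining half of it. Without that, power at the stated sizes is about 51% at prescriber level, Φ(0.34/0.1713 − 1.96), and 57% to 59% at patient level. This is a separate matter and is not caused by cutting. Below I take the 80% at face value, then test that choice in step 6.

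**3. Information kept by a cut.** For a normal moderator cut at c = z(q), the squared correlation between the cut and the original variable is

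eff = φ(c)² / [q(1 − q)].

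- q = 0.5: 0.3989²/0.25 = 0.637
- q = 0.3: 0.3477²/0.21 = 0.576
- q = 0.2: 0.2800²/0.16 = 0.490

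The loss is therefore 36%, 42% and 51%. At prescriber level the two ends equal about 110 to 150 of the 300 prescribers.

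**4. Power if the effect is linear.** If the binary test has 80% power, the continuous test of the same effect has power Φ(2.802/√eff − 1.96).

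| Split at the cut | eff | Binary test (as stated) | Continuous test |
|---|---|---|---|
| 50/50 | 0.637 | 80% | Φ(1.55) = 94% |
| 30/70 | 0.576 | 80% | Φ(1.73) = 96% |
| 20/80 | 0.490 | 80% | Φ(2.04) = 98% |

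**5. Power if the effect is a true step at the cut.** The binary test is then the efficient one. The linear test has power Φ(2.802 × √eff − 1.96) = 61%, 57% and 50% for the same three splits. The advantage depends on the shape of the interaction.

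**6. If the 80% is not taken at face value.** Starting from the lower power in step 2 (2 patients, 50/50 split), a linear effect gives these results.

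- Prescriber level: Φ(1.985/0.798 − 1.96) = 70%, against 51%.
- Patient level: Φ(2.195/0.798 − 1.96) = 79%, against 59%.

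The share of information lost is the same whatever the starting power. These are normal approximations to the interaction test, not simulations of the mixed logistic model.

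**The case against.** **A reader might infer that cutting drags the stated 80% down to between 50% and 61%.** The documents do not support this. Those values arise only if 80% is taken as the power of a continuous test and then discounted. Section 9.1 attaches its 80% to binary moderators at both levels, so the loss is already inside it and would be counted twice. The 51% to 59% in step 2 of the working looks similar by coincidence and comes from unstated inputs.

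**A reader might also infer that prior DOAC volume is cut at a single point, or that these are the trial's weakest tests.** Section 9.3.5 gives no cut for prior volume. Section 9.1 states 63% power for the adverse-event comparison, below the 80% stated for moderators.

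**A step is plausible, because dosing criteria are thresholds.** This has force, and step 5 shows what it would cost. But the documents' own thresholds lie elsewhere. The sample notification in Section 2.1 scores age at 80, the sample alert there refers to creatinine clearance below 30, and the examples in Section 8.4.2.2 change category between 51 and 48. None sits at age 70 or clearance 60, and no threshold for medication count appears outside the moderator list. Steps at other points would also violate linearity, which is why a flexible check is needed.

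**What stands.** The three patient-level cuts are pre-specified, which guards against data-driven choice. The renal cut has a clinical label, and any future EHR rule would need a threshold. The analysed patients are those who triggered an alert or notification, so creatinine clearance need not be normal among them. The analysis is exploratory, and nothing in the trial itself routes messages by these cuts.

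**Conclusion.** The point holds as a low-priority, inexpensive improvement. Three numeric moderators are tested only as cuts, and a fourth has no operational definition. Under a graded effect, with the normality, linearity and 20% to 50% split assumed above, cutting costs about 36% to 51% of the information. On the plan's own 80%, keeping the variables continuous would raise power to about 94% to 98%. The size rests on assumptions the documents neither state nor contradict, and the benefit disappears if the effect is a step exactly at the cut.

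The finding does not show that Section 9.1 overstates power because of dichotomising, and it does not touch the primary or secondary comparisons.

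**What to change.** **Section 9.3.5.** For age, creatinine clearance, concurrent medication count and prior six-month DOAC volume, make the test the treatment-by-continuous-moderator interaction in the same mixed logistic model.

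- Enter age and creatinine clearance linearly.
- Enter the two counts as log(1 + count). The offset matters because a prescriber could have no DOAC prescriptions in the prior six months, and the log of zero is undefined.
- Add a restricted cubic spline, with knots fixed in advance, as a check on linearity.
- Keep 70+, 5+ and 60 ml/min or less only for presenting subgroup estimates.
- Leave primary care versus specialist and VTE versus AF as binary.

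**Section 9.1.** State that the binary-moderator detectable effects apply only to the truly binary moderators.

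**Cost.** SAP wording only: the variables come from the EHR in any case and the model is otherwise unchanged. The price is a linearity assumption, checked by the spline, and slightly less simple reporting.
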